## **2. STATISTICAL METHODS**

This section describes the planned statistical analyses for the study. A detailed Statistical Analysis Plan (SAP) will be developed that outlines the methodology used in the statistical analyses described below.

### **2.1. Study Hypothesis**

There is no formal statistical hypothesis for this study.

### **2.2. Sample Size Considerations**

The sample size is based on potential adequacy of data to meet the study objectives; it is not based on any statistical consideration.

### **2.3. Data Analysis**

The analysis population consists of all subjects who have been treated with the study device as defined in Section 5.2.3.

Data collected in this study will be summarized using descriptive statistics. Summary statistics will include frequency counts and percentages for categorical variables and mean, standard deviation, minimum, median, and maximum for continuous variables.

- Reduced number of embolization devices required per procedure, potentially resulting in reduced procedural time and fluoroscopy exposure

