## 1. PROTOCOL SUMMARY

Title:	A Prospective, Multi-Center, Single-Arm, Real World Study Assessing the Clinical Use of the Caterpillar™ Arterial Embolization Device for Arterial Embolization in the Peripheral Vasculature
Sponsor:	Bard Peripheral Vascular, Inc. [name]
Objectives:	The primary objective of this study is to evaluate the performance and safety of the Caterpillar™ Arterial Embolization Device when used for arterial embolization in the peripheral vasculature in a real world, on-label application.
Design:	The post-market study is a prospective, multi-center, single-arm, real world study of the Caterpillar™ Arterial Embolization Device. Follow-up for all treated subjects will be performed at 30 days, as well as 6 and 12 months post-Index Procedure.
Study Device:	
The Caterpillar™ Arterial Embolization Device (Caterpillar™ Micro and Caterpillar™) is a self-expanding arterial occlusion plug, intended for arterial embolization in the peripheral vasculature. The device is intended to be a permanent implant and consists of the following components: a cobalt-chrome stem, nickel-titanium fibers, platinum-iridium radiopaque marker bands and a polyurethane and polyethylene occlusion membrane.
 
The Caterpillar™ Arterial Embolization Device is packaged as a single unit with the implant, loader, dispenser hoop, detachable delivery wire and torque tool. The device is intended for single-use only within a specific arterial vessel size range and does not require oversizing. The available sizes, product characteristics, intended arterial vessel diameter range and required delivery catheter size (inner diameter (ID)) are provided in the Instructions for Use (IFU).

Enrollment:	Enrollment will continue until up to fifty (50) subjects have been treated with the Caterpillar™ Arterial Embolization Device.
Study Sites:	Up to 20 investigational sites in the United States.
Study Population:	Male or non-pregnant female subjects ≥18 years of age who require arterial embolization in the peripheral vasculature.

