Secondary Endpoints:	
Time Point of Occlusion The percentage of target embolization site(s) with occlusion at ≤1, ≤2, ≤3, ≤4, ≤5, ≤10 and >10 minutes post-treatment.
 
Freedom from Recanalization Freedom from clinically relevant recanalization of the target embolization site(s) through 30-days, 6 and 12-months follow-up as confirmed by the Investigator. Clinically relevant recanalization is defined as recanalization through the study device that requires a re-intervention. Freedom from recanalization will be reported for each target embolization site.
 
Freedom from Migration Freedom from Migration will be reported for each study device as follows:
 

• Freedom from clinically relevant acute migration of the study device(s) as confirmed by the Investigator via angiographic assessment during the Index Procedure. Clinically relevant migration is defined as migration of the study device from the target embolization site that requires intervention.

• Freedom from clinically relevant migration of the study device(s) through 30-days, 6 and 12-months follow-up as confirmed by the Investigator. Clinically relevant migration is defined as migration of the study device from the target embolization site that requires a re-intervention.

 
Freedom from Device and/or Procedure-Related Adverse Events Freedom from device and/or procedure-related adverse events (AE) through 30-days, 6 and 12-months follow-up.
 
Accuracy of Delivery Accurate delivery of the study device to the target embolization site as assessed by the Investigator.
 
Ease of Trackability/Deliverability Ease of study device trackability and deliverability as assessed by the Investigator.
 
Ease of Detachment Ease of study device detachment as assessed by the Investigator.
 
Acceptability of Visibility Acceptability of study device visibility under fluoroscopy as assessed by the Investigator.

-----------------------------	---

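### Section 2.3 names counts and percentages for endpoints that run through 6 and 12 months, with no time-to-event method, denominator or rule for loss or death, so incomplete follow-up biases the percentages by a small amount whose direction depends on the denominator used

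*Combined protocol and SAP*

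**What the plan says.** Section 2.3 (Data Analysis) makes the analysis descriptive and states: "Summary statistics will include frequency counts and percentages for categorical variables". The population is given as: "The analysis population consists of all subjects who have been treated with the study device as defined in Section 5.2.3". Section 5.2.3 is not in the text available for this review. Section 2 adds: "A detailed Statistical Analysis Plan (SAP) will be developed that outlines the methodology used in the statistical analyses described below".

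The Protocol Summary sets the schedule: "Follow-up for all treated subjects will be performed at 30 days, as well as 6 and 12 months post-Index Procedure". Three secondary endpoints are cumulative over that schedule:

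- Recanalization, by site: "Freedom from recanalization will be reported for each target embolization site".
- Migration, by device: "Freedom from Migration will be reported for each study device as follows".
- Adverse events, with times but no reporting unit: "Freedom from device and/or procedure-related adverse events (AE) through 30-days, 6 and 12-months follow-up".

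Inclusion criterion 2 and exclusion criterion 13 ask for a life expectancy long enough to collect the primary endpoint data. The longest primary endpoint window is 30 days. The available text has no time-to-event method, censoring rule, endpoint denominator, or rule for subjects who are lost or die before 6 or 12 months.

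**The concern.** The eligibility criteria protect follow-up to 30 days, while these endpoints run to 12 months, so some incomplete late follow-up is foreseeable. A percentage then needs a decision about subjects whose status at 12 months is unknown. Counting them as event-free ignores any event after loss. Dropping them while keeping every observed event removes only event-free people from the denominator. The text does not choose between these, so two analysts could report different figures from the same data and both could claim to follow Section 2.3.

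These endpoints are the study's only evidence on device durability and its only safety results beyond 30 days. In a descriptive study the reported percentages are themselves the result. If no events occur, a bare 100% does not show how many subjects were followed to 12 months, or whether deaths were counted as event-free.

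**Working it through.** **Inputs from the documents.** Up to 50 treated subjects; up to 5 sites and 10 devices per subject; contacts at 30 days, 6 and 12 months. The documents give no event, loss or death rate and no expected freedom, so there is no figure of the plan to reproduce.

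**Assumed inputs.** 12-month event risk e and 12-month loss d, constant hazards, loss independent of the event. Middle case: e = 10%, d = 20%.

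**Formulas**, with t in years, λ = −ln(1−e), μ = −ln(1−d):

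- True freedom: exp(−λt)
- Observed event share: E = λ/(λ+μ) × [1 − exp(−(λ+μ)t)]
- Followed to t without event: C = exp(−(λ+μ)t)
- All treated, lost counted as event-free: 1 − E
- Lost dropped, events kept: C/(C+E)

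**Middle case at 12 months.** λ = 0.1054, μ = 0.2231, C = 0.9 × 0.8 = 0.72, E = (0.1054/0.3285) × 0.28 = 0.0898. All treated: 1 − 0.0898 = 91.0%. Dropped: 0.72/0.8098 = 88.9%. True value: 90.0%. Counting the lost as failures would give 72.0%.

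| e / d | True | All treated | Dropped |
|---|---|---|---|
| 2% / 20% | 98.0 | 98.2 (+0.2) | 97.8 (−0.2) |
| 5% / 10% | 95.0 | 95.3 (+0.3) | 94.7 (−0.3) |
| 10% / 20% | 90.0 | 91.0 (+1.0) | 88.9 (−1.1) |
| 20% / 40% | 80.0 | 84.2 (+4.2) | 75.2 (−4.8) |

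At 6 months the middle case gives 95.1 and 94.6 against 94.9.

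**Event timing.** For any timing under independent loss, the all-treated error is the probability of being lost first and then having the event by 12 months. It lies between 0 and e × d, here 0 to +2.0 points. The dropped error lies between 0 and 0.72/(0.72 + 0.10) − 0.90 = −2.2 points. With half the event risk in the first 30 days, the two results are 90.60 and 88.45; with all of it there, 90.09 and 87.90. Early events therefore shrink the all-treated error and enlarge the dropped one.

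**30 days.** Even at 20% / 40%, the results are 98.22 and 98.14 against 98.18, an error of 0.04 points.

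**Informative loss.** If the event hazard triples after loss in the middle case, a further 2.85% have an unseen event and true freedom is 1 − 0.0898 − 0.0285 = 88.2%. All-treated is then +2.9 points and dropped +0.7. Kaplan-Meier still targets 90.0%, an error of +1.8. Over 5–20% events and 10–30% loss, all-treated errs by +0.7 to +8.0 and dropped by +0.2 to +1.7.

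**Deaths.** Add 10% mortality (κ = 0.1054). One minus cumulative incidence is 1 − 0.5 × (1 − 0.81) = 90.5%. The all-treated percentage is 91.45%.

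**In whole subjects.** Take 50 treated, events at 2, 4, 7 and 10 months, and 10 losses spread evenly from 0.9 to 10.8 months. All-treated is 46/50 = 92.0%, dropped is 36/40 = 90.0%, and Kaplan-Meier is 48/49 × 45/46 × 41/42 × 37/38 = 91.1%.

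**Site level.** A simulation (8,000 runs, 50 subjects, 1–5 sites each, loss by subject, e = 10%, d = 20%) gives Kaplan-Meier 90.0, all-treated 91.0 and dropped 88.9, the same shifts as per subject. A shared frailty with variance 2 raises the standard deviation of the estimate from 2.6 to 3.1 points.

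**No events.** The exact lower 95% limit is 0.025^(1/n): 92.9% for 50/50, 91.2% for 40/40, 88.4% for 30/30. This applies to the adverse event endpoint if its unit is the subject.

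**The case against.** The case for leaving the plan alone has four parts.

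- **Nothing is excluded.** Section 2.3 says what summaries will include, and a Kaplan-Meier curve is itself descriptive. A reader might infer that percentages are the only method planned. The wording does not say so, Section 5.2.3 is not available, and a SAP is to follow. This stands: the gap can be asserted only for the available text.
- **The direction is not fixed.** A reader might infer that the plan will overstate freedom. Without a denominator rule that does not follow, since dropping the lost understates it under independent loss. This also stands. Naming all treated subjects as the population makes the overstating reading the closest one, but does not settle it.
- **The effect is small and the rates are assumed.** With 50 subjects, one subject is 2 points, and the binomial standard error at 90% is √(0.9 × 0.1/50) = 4.2 points. Recanalization and migration count only if they need an intervention, so events may be rare. Inclusion criterion 3, exclusion criterion 13 and the option of telephone contact should limit loss. As Section 2.1 says, "There is no formal statistical hypothesis for this study". All of this stands and limits the weight of the point.
- **Kaplan-Meier also assumes independent loss.** True: in the tripled-hazard example it errs by +1.8 points, more than the dropped rule does there. It still errs less than the all-treated percentage, and its assumption is explicit.

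What remains is that each simple percentage has a systematic error under independent loss that a standard method avoids, and that the choice between them is open.

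**Conclusion.** The point holds as a cheap improvement for the 6- and 12-month results. Under independent loss with constant hazards, and at an assumed 10% event risk and 20% loss, the 12-month shift is +1.0 point with lost subjects counted as event-free and −1.1 with them dropped. It is about 0.2 points either way at 2% events, and reaches +4.2 or −4.8 only at 20% events with 40% loss, which nothing in the documents suggests. These figures illustrate the size and are not bounds; informative loss can enlarge the overstatement and reverse the sign for the dropped rule.

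A reader might go further and infer that the primary safety endpoint or some study conclusion is compromised. The documents do not support that: its window closes at 30 days, where the error is negligible, and no test or success threshold rests on the later percentages.

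**What to change.** In Section 2.3 or the SAP:

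- Estimate 6- and 12-month freedom from recanalization, migration and device- or procedure-related adverse events by Kaplan-Meier from the Index Procedure, censoring subjects lost alive at last contact. State that censoring is assumed independent of the event.
- State how deaths are handled, for example one minus cumulative incidence with death as a competing event, which equals Kaplan-Meier if no one dies.
- State the reporting unit for the adverse event endpoint.
- Report numbers at risk, lost and dead at each time point.
- Let any site- or device-level interval allow for clustering within subject. Intervals are optional here.

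Counts and percentages can stay for the procedural and 30-day results.

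The cost is a few sentences and slightly more programming. Dates of event, death and last contact are needed; the available text does not show these fields, so confirm that they are collected. The independence assumption cannot be checked from the data, and 12-month intervals, if given, will be wide. If the full protocol or the later SAP already has such a rule, a cross-reference closes the point.
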